#### **4.4.2.4 Cervarix Seroconversion**

Seroconversion 28 days after each dose is defined as changing serostatus from seronegative at baseline to seropositive ( $>$  LLOQ of the assay) or  $\geq 4$ -fold rise in Ab titer if seropositive at baseline.

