## 5.1 Statistical Methods

In a general way, non-inferiority testing will be performed on dengue immune subjects. The tests will be done only if the number of evaluable subjects provides a global power of at least 80% for the co-primary objectives and secondary objective. In case the global power is insufficient to perform non-inferiority testing, only descriptive analyses will be performed.

Only descriptive analyses will be conducted in dengue non-immune subjects and in the overall population.

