### 5.1.1 Hypotheses and Statistical Methods for Primary Objectives

#### 5.1.1.1 Hypotheses

##### ***Non-inferiority on Cervarix***

The objective is to demonstrate that the humoral immune response to Cervarix administered concomitantly with CYD dengue vaccine is non-inferior to the immune response to Cervarix administered sequentially with CYD dengue vaccine.

Individual hypotheses on Cervarix response for each antigen:

A non-inferiority testing approach will be used to compare geometric mean of titer (GMTs) for the 2 antigens (HPV-16 and HPV-18) 28 days after the last dose of Cervarix, based on the following individual hypotheses:

$$H_0^i: \text{GMT}_{\text{Group1}}^i / \text{GMT}_{\text{Group2}}^i \leq \frac{1}{\delta} \Leftrightarrow \log_{10}(\text{GMT}_{\text{Group1}}^i) - \log_{10}(\text{GMT}_{\text{Group2}}^i) \leq -\log_{10}(\delta)$$

$$H_1^i: \frac{1}{\delta} < \text{GMT}_{\text{Group1}}^i / \text{GMT}_{\text{Group2}}^i > \frac{1}{\delta} \Leftrightarrow \log_{10}(\text{GMT}_{\text{Group1}}^i) - \log_{10}(\text{GMT}_{\text{Group2}}^i) > -\log_{10}(\delta)$$

with:

i, antigen (HPV-16 and HPV-18)

$\delta$  non-inferiority limit is set at 2, ie, 0.301 ( $=\log_{10}[2]$ ), for each antigen "i"

Non-inferiority for antigen i will be demonstrated if the lower bound of the 2-sided 95% CI is greater than  $-\delta$  ( $\alpha=2.5\%$  one-sided).

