#### **5.1.2 Hypotheses and Statistical Methods for Secondary Objectives**

##### **5.1.2.1 Hypotheses**

###### ***Non-inferiority on Cervarix***

The objective is to demonstrate that the humoral immune response (in terms of seroconversion) to Cervarix after concomitant administration with CYD dengue vaccine is non-inferior to sequential administration with CYD dengue vaccine measured 28 days after the last dose of Cervarix.

A non-inferiority testing approach will be used to compare seroconversion rates for the 2 antigens (HPV-16 and HPV-18) 28 days after the last dose of Cervarix.

The individual tested hypotheses for the antigen “i” will be as follows:

$$H_0^i: P_{Group1}^i - P_{Group2}^i \leq -\delta$$

$$H_1^i: P_{Group1}^i - P_{Group2}^i > -\delta$$

where the non-inferiority limit  $\delta$  is set at 5% for each antigen “i”.

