#### **5.1.2.2 Statistical Methods**

##### ***Non-inferiority on Cervarix***

Non-inferiority for antigen “i” will be demonstrated if the lower bound of the 2-sided 95% CI is greater than  $-\delta$ .

The non-inferiority test will be performed using the 95% 2-sided CI of the difference between groups ( $\alpha=2.5\%$  one-sided). The 95% CI will be calculated based on the Wilson score method without continuity correction as quoted by Newcombe for seroconversion rates.

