#### **PPX**

The subjects presenting with at least one of the following relevant protocol deviations will be excluded from the PPX:

- Subject did not meet all protocol-specified inclusion criteria or met at least one of the protocol-specified exclusion criteria
- Subjects identified as dengue non-immune subjects (seronegative) at baseline
- Subject is seropositive at baseline for Cervarix (ie, at least one Ab levels against Cervarix HPV antigens > LLOQ at baseline)
- Subject did not complete the Cervarix vaccination schedule (until V05 for Group 1, V06 for Group 2)
- Subject received a vaccine other than the one that she was randomized to receive (until V05 for Group 1, V06 for Group 2)
- Administration of vaccine was not done as per-protocol (site and route of administration)

- Subject did not receive vaccine in the proper time window (until V05 for Group 1, V06 for Group 2)
- Subject did not provide after the 2nd dose of Cervarix a post-dose serology sample in the proper time window or a post-dose serology sample was not drawn (V05 for Group 1, V06 for Group 2)
- Subject received a protocol-prohibited medication (prohibited therapies/medications/vaccines are indicated in the Protocol Section 6.7) (until V05 for Group 1, V06 for Group 2)
- Subject's serology sample did not produce a valid test result, ie, no Cervarix antigen titer available

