## 5.2.5 Populations Used in Analyses

The main immunogenicity analyses (non-inferiority tests) will be performed on the per protocol analyses sets PPX and PPC respectively for Cervarix and CYD dengue vaccine comparisons. The subjects will be analyzed by the vaccine group to which they were randomized.

All other immunogenicity analyses will be performed on the FAS and by baseline dengue status. Subjects will be analyzed by the vaccine group to which they were randomized.

The safety analyses will be performed on the SafAS. Subjects will be analyzed according to the vaccine they actually received and by baseline dengue status.

Complementary analyses on Zika and FV baseline statuses (and by baseline dengue status) will be performed on randomized subjects and on the FAS.

Dengue GMTs by Zika and by FV baseline statuses by Zika baseline status will be performed on all subjects and on FAS dengue immune subjects.

Description of immune response to each dengue serotype according to Zika status at baseline will be performed on FAS dengue immune subjects.

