### **5.5 Determination of Sample Size and Power Calculation**

A total of 480 subjects will be enrolled: 240 subjects in each group.

The reference standard deviations (SD) considered for Cervarix are 0.4 for both HPV-16 and HPV-18.

The reference seroconversion rates for Cervarix were set to 99% for both antigens.

The reference SD considered are the following for CYD dengue vaccine: 0.9 for serotype 1, 0.7 for serotypes 2 and 3 and 0.5 for serotype 4 (based on CYD13 and CYD15 efficacy studies conducted in subjects aged 9 to 16 years in Latin American countries).

Considering a potential attrition rate of 15%, such sample size would provide 204 evaluable subjects in the per protocol (PP) population per group. This will give, for the co-primary objectives, a global power of 90.2% and for secondary objectives (in terms of Cervarix seroconversion) a power of 91.8%.

Following Protocol Amendment 1, the number of evaluable subjects may be difficult to achieve (considering only dengue immune (seropositive) subjects at baseline to be included in the Per-Protocol populations). Thus the non-inferiority testing will be done only if the number of evaluable subjects provides a global power of at least 80% for the co-primary objectives and secondary objective ie, if the number of evaluable subjects is at least 163 per group for the co-primary objectives and 168 per group for the secondary objective. The power for non-inferiority in terms of GMTs per antigen and serotype is detailed in Table 5.1 and Table 5.3.

This initial study sample size will also provide a 95% probability of observing an AE that has a true incidence of 1.2% in each group (regardless of baseline serostatus).

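### PPX drops a girl from both HPV comparisons if she is above LLOQ for either type at baseline; an antigen-specific rule would protect the 168-per-group seroconversion gate at little cost

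*SAP*

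**What the plan says.** One per-protocol set, PPX, covers both Cervarix antigens. SAP 5.2.2 removes from it anyone who meets this criterion: "Subject is seropositive at baseline for Cervarix (ie, at least one Ab levels against Cervarix HPV antigens > LLOQ at baseline". Protocol 12.2.2 has the same rule. Neither document gives a reason for making it joint, and neither has an antigen-specific version.

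SAP 5.2.5 says that the non-inferiority tests "will be performed on the per protocol analyses sets PPX and PPC respectively for Cervarix and CYD dengue vaccine comparisons". The hypotheses are stated separately for HPV-16 and HPV-18. For GMTs (SAP 5.1.1.1) the "non-inferiority limit is set at 2, ie, 0.301" on the log10 scale. For seroconversion (SAP 5.1.2.1) the margin "is set at 5% for each antigen".

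Testing depends on numbers. SAP 5.5 allows it only "if the number of evaluable subjects is at least 163 per group for the co-primary objectives and 168 per group for the secondary objective". SAP 5.1 adds: "In case the global power is insufficient to perform non-inferiority testing, only descriptive analyses will be performed".

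Baseline HPV serology is not an entry criterion. Protocol 5.2.5 excludes on reported HPV history and prior HPV vaccination only, and HPV blood is drawn from both groups at V01 (Protocol Table 7.1). Antibody-positive girls can therefore be enrolled, vaccinated and sampled.

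**The concern.** A girl above LLOQ for HPV-16 alone is naive to HPV-18, so her HPV-18 response is as informative as that of any other naive girl. The joint rule still removes her from the HPV-18 test. Excluding her from the HPV-16 test alone would keep the tested population naive to the tested antigen.

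This would be a minor inefficiency if numbers were ample. After Amendment 1 they are not: only dengue-immune girls count, SAP 5.5 itself warns that the numbers may be hard to reach, and the count decides whether the seroconversion hypothesis is tested or only described. The 15% attrition allowance contains no separate item for HPV seropositivity.

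**Working it through.** **Inputs from SAP 5.5 and 5.1.2.1.** Seroconversion 99% in both groups; margin 0.05; one-sided alpha 0.025; 204 per group after attrition (240 × 0.85); gate 168 per group; HPV SD 0.4 on log10.

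**Reproducing the seroconversion power.** I used the Farrington-Manning score method:

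power = Φ[(0.05 − 1.96·√(V0/n)) / √(V1/n)]

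Here V1 = 2 × 0.99 × 0.01 = 0.0198. V0 uses the rates fitted under the null difference of −0.05, which are 0.9446 and 0.9946, so V0 = 0.0576. Squaring gives the global power over two antigens.

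| n per group | per antigen | global | plan |
|---|---|---|---|
| 204 | 95.8% | 91.8% | 95.8% / 91.8% |
| 180 | 92.3% | 85.1% | – |
| 168 | 89.6% | 80.4% | 89.6% / 80.4% |
| 167 | 89.4% | 79.9% | – |
| 162 | 88.1% | 77.6% | – |

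The plan's figures reproduce, and 168 is the smallest n that reaches 80%. The gate therefore has no slack by this method.

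**Where the rule does not bite.** With SD 0.4, the HPV GMT confidence interval has a half-width of 1.96 × 0.4 × √(2/162) = 0.087, against a margin of 0.301. Both HPV GMT tests together reach 80% power at 38 per group. The figure of 163 comes from dengue: 0.853 × 0.972² × 0.999³ = 0.803, where 0.853 is serotype 1. Dengue is tested on PPC, which has no HPV-baseline exclusion.

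**Size of the loss (assumed prevalence).** The documents give no baseline HPV seroprevalence, so let each type have prevalence p. With independent types the joint rule keeps (1 − p)² and the antigen-specific rule keeps (1 − p). The share naive to the tested antigen but lost is p(1 − p). It is zero if the types overlap fully and p if they never overlap. The last two columns give the otherwise evaluable girls per group needed to reach 168.

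| p per type | needlessly lost | joint: left of 200 | specific: left of 200 | joint: needed | specific: needed |
|---|---|---|---|---|---|
| 2% | 2.0% | 192 | 196 | 175 | 172 |
| 5% | 4.8% | 180 | 190 | 187 | 177 |
| 10% | 9.0% | 162 | 180 | 208 | 187 |

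The choice of rule changes the gate result only when the otherwise evaluable count lies between the two requirements: 172–174 at 2%, 177–186 at 5% and 187–207 at 10%.

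**In terms of dengue serostatus.** With 204 per group after attrition, reaching 168 needs 168/204 = 82.4% dengue-seropositive before any HPV exclusion. At p = 5% this becomes 168/(204 × 0.9025) = 91.2% under the joint rule and 168/(204 × 0.95) = 86.7% under the specific rule. At p = 10% it becomes 101.7%, which is impossible, against 91.5%.

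**The case against.** The strongest defence is that a fully HPV-naive set is a coherent choice. Protocol 5.2.5 already bars reported HPV infection of any type and any prior HPV vaccination. The global hypothesis also requires both antigens to succeed, so one common population is natural. This stands as a possible rationale, but the plan does not state it, and naivety to the other type is not needed for a valid test of either antigen.

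Second, the benefit cannot be sized from the documents. Prevalence and overlap are assumptions, and the windows in which the gate result changes are narrow at low prevalence. This stands. The illustrative 200 otherwise evaluable per group is also close to the planned 204, so it presumes that nearly all girls are dengue-seropositive.

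Third, the gate is a head count. By exact enumeration of the planned Newcombe-Wilson interval, global power is 84.0% at 168 and still 0.906² = 82.0% at 162. This stands too: failing the gate in the example would stop a test that had adequate power under the planned interval.

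Fourth, the girls are not lost altogether. They stay in the FAS descriptions, where the seroconversion branch for a "fold rise in Ab titer if seropositive at baseline" can apply. They are, however, in no planned non-inferiority test. Protocol 12.2.5 would have confirmed the tests on the FASE, which keeps them, but SAP 5.7 drops that set and SAP 5.2.5 names no replacement.

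A reader might infer more than this, and the documents do not support it:
- **Bias between groups.** The criterion is a pre-vaccination value applied equally in both groups, so it costs numbers and does not by itself bias the comparison.
- **Risk to the co-primary objectives.** HPV GMT power exceeds 99.9% at these sizes, and the 163 requirement comes from dengue serotype 1 on PPC. The plan does not say in which set 163 is counted, but the Cervarix GMT tests do not need that number.
- **A material loss of precision in all four HPV comparisons.** For the two GMT comparisons the loss is trivial against the margin.

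**Conclusion.** The joint exclusion removes girls from the test of an antigen to which they are naive, and this can matter for the seroconversion test and its gate of 168 per group. With independent types, the needless loss per test is 2.0%, 4.8% and 9.0% of otherwise evaluable girls at assumed prevalences of 2%, 5% and 10% per type; it falls to zero with full overlap. At 200 otherwise evaluable per group and 10% per type, the rule decides the gate: 162 (77.6% global power, failed) against 180 (85.1%, passed). At 2% or 5% the same 200 pass under either rule.

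These figures rest on the assumed prevalence and independence, on equal prevalence for the two types, and on the plan's convention of multiplying power across antigens. The rule is not an error in the analysis. Changing it is a small, cheap improvement that recovers subjects already vaccinated and sampled.

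**What to change.** Before database lock, reword the PPX criterion in SAP 5.2.2 to: 'For the HPV-16 (HPV-18) comparison, exclude subjects with HPV-16 (HPV-18) antibody > LLOQ at baseline.' State in SAP 5.5 that the smaller of the two per-antigen counts is compared with the 168 gate. Report the number analysed for each antigen. Record the change from Protocol 12.2.2 in SAP 5.7, with the reason, because relaxing a per-protocol criterion in an open-label trial should be visibly independent of the results.

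The cost is one sentence, one flag per antigen, two slightly different denominators in the Cervarix tables and a documented departure from the protocol. No new data are needed. If the sponsor prefers one fully naive set, the alternative is to state the reason for it.

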
Schedule of Study Procedures:
 
At the time of Protocol Amendment 1, all subjects have completed V05 (Group 1) or V06 (Group 2). Dengue unexposed subjects will not receive further dengue vaccine injections. If a subject and the subject's parents/ legally acceptable representative consent to continue participating in the study, they will sign the Assent Form (AF) / Informed Consent Form (ICF). All unexposed subjects that consent to continue participating in the study will be contacted by phone for a safety follow-up 6 months after the last injection. They will not attend any further study visits (except the unscheduled visit and/or the next scheduled visit planned to sign the ICF/AF).
 
For dengue exposed subjects who consent to continue in the study and to receive the next CYD dengue vaccine injection, study procedures will proceed as planned in the original protocol.
 
Visits/phone call :
 
Subjects will have 6 (Group 1) or 8 (Group 2) visits. Subjects will be contacted by phone 7 days after each injection and 2 months after blood samples during the 6-month period after each vaccination. The last phone call will be for the 6-month follow-up after the last injection of CYD dengue vaccine.
 
An unscheduled visit or phone call will take place during the study pause in order to communicate the new data on the CYD dengue vaccine to each subject. This visit will be before the next visit initially planned (V07 for most subjects; V08 for 2 subjects). Dengue serostatus at baseline may be communicated to the subjects, if available, at the time of the unscheduled visit. If not available at the time of the unscheduled visit, the dengue serostatus at baseline will be communicated at the next planned visit.
 
Vaccination:
 
See Table S1.
 
Group 1: Cervarix and CYD dengue vaccine (concomitantly) at D0 and M6, and CYD dengue vaccine (alone) at M12
 
Group 2: Cervarix (alone) at D0 and M6, and CYD dengue vaccine (alone) at D0+28D (M1), M6+28D (M7), and M12+28D (M13)
 
Blood sampling:
 
Subjects will provide:
 
• 4 mL, for CYD dengue vaccine immunogenicity assessments by dengue neutralizing Abs (4 mL) before the first vaccination (at D0 in Group 1, and M1 in Group 2) and 28 days after each vaccination with the CYD dengue vaccine• 2 mL, for HPV immunogenicity assessments by cLIA before the first vaccination (at D0) and 28 days after each vaccination with Cervarix 
See Table S 1 for details on timings.
 
Additional blood samples that may be collected at any time throughout the study period, regardless of the subject's dengue serostatus:
 
• In the event of a hospitalized suspected dengue case (3 mL approximately), within the first 5 days after fever onset (or as soon as possible if not within the 5 days), for virological confirmation by NS1 Ag ELISA, and/or WT dengue RT-PCR.• In the event of SAEs (including AESIs).• To assess AEs that may be indicative of viscerotropic or neurotropic disease (see Guidelines for Assessing Viscerotropic and Neurotropic AE).	

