--	--

	
objectives and 168 per group for the secondary objective.
 
Interim analysis:
 
Two planned statistical analyses will be performed:
 
An interim statistical analysis of the data obtained up to Day 28 post third CYD dengue vaccination might be performed once data are available and a database lock has been conducted.
 
A final analysis will be performed once the 6 month safety data have been collected and the final database lock has occurred.
 
No statistical adjustment is necessary because there will be no repeated analyses of the primary objective (as the test will be performed at the time of the first analysis).

--	---

Table of Study Procedures

Phase IIIb Trial; 5 Injections; **Group 1**: 6 Visits and a 6-month follow-up Phone Call, 4 Blood Samples, 18 Months duration per subject, 6 interim phone calls; **Group 2**: 8 Visits and a 6-month follow-up Phone Call, 6 Blood Samples, 19 Months duration per subject, 8 interim phone calls. Interim phone calls will be given 7 days after each injection (PC1, PC2, PC4, PC5, and PC7) and 2 months after blood samples (PC3, PC6, and PC8) during the 6-month period after each vaccination. As per Protocol Amendment 1, only dengue-exposed subjects before the first dengue vaccine injection will be eligible to continue study vaccinations with the CYD dengue vaccine.

Visit (V) Number	Time period prior to Protocol Amendment 1						Time period post Protocol Amendment 1*		
	V01	V02	V03 (Group 2)	V04	V05	V06†‡ (Group 2)	V07**	V08†	Phone Call§
Trial Timelines	D0	M1 (V01+28D)	M2 (V02+28D)	M6 (V01 + 6M)	M7 (V04+28D) (Group 1) (V02+6M) (Group 2)	M8 (V05+28D)	M12 (V01 + 12M) (Group 1) M13 (V02+ 12M) (Group 2)	M13 (V07+28D) (Group 1) M14 (V07+28D) (Group 2)	M18 (V07+6M) (Group 1) M19 (V07+6M) (Group 2)
Time Windows (days)		+14	+14	±20	+14	+14	±20	+14	+30
Informed Consent and assent form (if applicable) signed	X								
Amendment 1 to AF and ICF						X (Amdt 1) (as applicable)	X (Amdt 1) (as applicable)		
Inclusion/Exclusion Criteria	X								
Significant Medical History	X								
History of Dengue Infection/Vaccination	X								
Demography/Body Stature	X								
Physical/Clinical Examination and Temperature**	X	X (Group 2)	X (Group 2)	X	X	X (Group 2)	X	X	
Concomitant Therapy††	X	X	X (Group 2)	X	X	X (Group 2)	X	X	
Urine Pregnancy Test‡‡	X	X (Group 2)		X	X (Group 2)		X		
Randomization	X								
Contraindications		X (Group 2)		X	X (Group 2)	X	X		

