‡ All subjects will either attend an unscheduled visit (V00) or have an unscheduled phone call (PC00) during the study pause and **before** the next scheduled visit (V07 for most subjects; V08 for 2 subjects). During the unscheduled visit or phone call, the subject will be informed about the new safety data thanks to a “dear participant letter” and on their baseline serostatus result. The signature of the ICF/AF by the parents/subjects and the check of contraindications to continue in the study will be performed at the next visit planned, as applicable.

§ The 6-month phone call will be given to all subjects who consented to continue in the study whether they were identified as “dengue-exposed” or “dengue unexposed”

** A full physical and clinical examination will be performed and documented on each vaccination visit (mandatory before vaccination) and at the Investigator’s discretion if necessary based on the health status of the subject for the other visits.

†† Concomitant therapy will be collected for Days 0–28 after each injection only

‡‡ In female subjects of childbearing potential. Result of urine pregnancy test should be confirmed as negative before vaccination.

§§ Blood samples planned during vaccination visits will be taken before vaccination

*** In such case, 1 unplanned acute blood sample (approximately 3 mL) will be collected for virological confirmation of dengue disease, by NS1 (nonstructural protein 1) antigen test (ELISA), and/or WT dengue RT-PCR

††† Interim phone calls will be given 7 days (+8 days of time window) after each injection (PC1: V01 + 7 days, PC2: V02 + 7 days, PC4: V04 + 7 days, PC5: V05 + 7 days, and PC7: V07 + 7 days) and approximately 2 months after blood samples (PC3: M3 or M4, PC6: M9 or M10, and PC8: M15 or M16) during the 6-month period after each vaccination.

††† MA will be delivered to subjects who will not receive further CYD dengue vaccine injection but consent to continue their participation in the study.

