5.1.2 Justification of the Trial Design

There is currently no data on concomitant administration of CYD dengue vaccine with other vaccines in the indicated population aged 9-45/60 years of age. Based on the current age indication of the CYD dengue vaccine, co-administration data with Cervarix, currently used in public sector school-based vaccination programs in females aged 9 years and above, could support implementation of school-based vaccination programs for CYD vaccine. Therefore, the present CYD71 study will investigate the immunogenicity and safety of the CYD dengue vaccine candidate when it is administered concomitantly or sequentially with Cervarix at least 28 days apart in female subjects aged 9 to 14 years.

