Subject’s participation in the study was expected to be of 18 or 19 months. Time for the approval of Protocol Amendment 1 by the competent authorities and completion of the associated logistic tasks will result in a hold of study activities (approximately 6 months), and thus, in an extension of study duration for dengue exposed subjects.

Blood Samples

Subjects will provide blood samples:

- for CYD dengue vaccine immunogenicity assessments by dengue neutralizing Abs (4 mL) before the first vaccination (at D0 in Group 1, and M1 in Group 2), and 28 days after each vaccination with CYD dengue vaccine (M1, M7 and M13 in Group 1, and M2, M8 and M14 in Group 2)
- for HPV immunogenicity assessments by ELISA (2 mL) before the first vaccination at D0, and 28 days after each vaccination with Cervarix (M1 and M7)

Additional biological samples that may be collected at any time throughout the study period, regardless of the subject’s dengue serostatus:

- for virological confirmation of hospitalized suspected dengue case within the first 5 days after fever onset (or as soon as possible if not within the 5 days) (approximately 3 mL) by NS1 Ag ELISA, and/or wild type (WT) dengue RT-PCR
- in the event of SAEs (including serious AEs of special interest [AESIs])
- to assess AEs that may be indicative of viscerotropic or neurotropic disease (see Guidelines for Assessing Viscerotropic and Neurotropic AE).

Urine samples

All subjects of childbearing potential will provide urine samples for urine pregnancy test before each injection.

A schedule of assessments and study vaccinations is provided in the [table of study procedures](#).

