- 4) Perform a urine pregnancy test before injection (for woman of childbearing potential only).
- 5) Review temporary and definitive contraindications to vaccination
- 6) Inject the second dose of Cervarix to all subjects (Groups 1 and 2) and the second dose of CYD dengue vaccine to subjects in Group 1 (6 months post-dose 1).
- 7) Keep the subject under observation for 30 minutes, and record any immediate AE in the source document.
- 8) Record the date of injection(s), the site and side of injection(s) and the route of administration(s), as well as the dose number of the vaccine(s).
- 9) Give the parent(s)/legally acceptable representative(s) a DC.
- 10) Remind the parent(s)/legally acceptable representative(s) to bring back the DC when they return for Visit 5 at a specified date and time.
- 11) Complete the relevant CRF pages for this visit.

Phone Call 4 (PC4) (7 [+8 days] days after Visit 4)

The same procedures as those described for PC1 will be followed.

Visit 5 (Month 7; 6 months /± 20 days/ after Visit 2)

The Investigator or designated study personnel will:

- 1) Review the pages of the DC with the parent(s)/legally acceptable representative(s), including any AEs, medications, or therapy that occurred since vaccination.
- 2) Perform a physical examination and record the subject's axillary temperature
- 3) Check concomitant medications and record every reportable medication ongoing at the time of vaccination.
- 4) Obtain the blood sample (see [Section 7.1](#) for detailed instructions regarding the handling of blood samples).
- 5) For female subjects of childbearing potential, perform a urine pregnancy test before injection (subjects in Group 2 only).
- 6) Review temporary and definitive contraindications to vaccination
- 7) Inject the second dose of CYD dengue vaccine to subjects in Group 2 (6 months post dose 1).
- 8) Keep the subject under observation for 30 minutes, and record any immediate AE in the source document (Group 2).
- 9) Record the date of injection, the site and side of injection and the route of administration, as well as the dose number of the vaccine (Group 2).

- 10) Give the parent(s)/legally acceptable representative(s) a DC for Group 2 and Group 1 (for Group 1 DC for SAE collection only).
- 11) Remind the parent(s)/legally acceptable representative(s) of subjects in Group 2 to bring back the DC when they return for Visit 6 at a specified date and time.

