9.1.1.2 Immunogenicity Assessment Methods

HPV Abs

The Ab response to HPV will be performed at Sanofi Pasteur GCI, Swiftwater, USA, or GCI outsourced laboratory. The HPV16/18 virus-like particle-based enzyme linked immunosorbent assay (VLP-ELISA) is performed using serial dilutions of serum samples and standards added to HPV VLP-coated ELISA microtiter plates. A peroxidase-conjugated anti-human IgG polyclonal antibody, enzyme substrate, and chromogen are added; reactions are then stopped. Optical density (OD) at 620 nm (background) is read and subtracted from OD at 450 nm. Antibody levels in ELISA units (EU)/mL are calculated by interpolating OD values from the standard curve.

This assay will be performed on blood samples taken from V01, V02 and V05.

Dengue Neutralizing Abs

Dengue neutralizing Ab levels will be measured by PRNT₅₀ (using parental dengue virus strains of CYD dengue vaccine constructs) by Sanofi Pasteur GCI, Swiftwater, USA (or outsourced with a GCI selected external laboratory).

Serial, two-fold dilutions of serum to be tested (previously heat-inactivated) are mixed with a constant challenge-dose of each dengue virus serotype 1, 2, 3 or 4 (expressed as plaque-forming unit [PFU]/mL). The mixtures are inoculated into wells of a microplate with confluent Vero cell monolayers. After adsorption, cell monolayers are incubated for a few days. The presence of dengue virus infected cells is indicated by formation of plaques. A reduction in virus infectivity due to neutralization by Ab present in serum samples is detected. The reported value (end point neutralization titer) represents the highest dilution of serum at which $\geq 50\%$ of dengue challenge virus (in plaque counts) is neutralized when compared to the mean viral plaque count in the negative control wells which represents the 100% virus load. The end point neutralization titers are presented as continuous values. The lower limit of quantitation (LLOQ) of the assay is 10 (1/dilution [dil]).

This assay will be performed on each blood samples taken at V01 (Group 1 only), V02, V03 (Group 2 only), V05 (Group 1 only), V06 (Group 2 only), and V08.

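### The Cervarix per-protocol set checks Group 2 at V06, a dengue-only draw, although the HPV endpoint sample is V05 in both groups; Group 2 alone can be excluded for events after its endpoint.

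*SAP*

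**What the plan says.** PPX, as defined in SAP 5.2.2, excludes a subject whose sample after the second Cervarix dose is outside its window, or when "a post-dose serology sample was not drawn (V05 for Group 1, V06 for Group 2". Protocol 12.2.2 has the same bullet. The same V05/V06 split is attached to four other PPX bullets: completion of the schedule, wrong vaccine, vaccination window and prohibited medication. The site/route bullet has no cut-off visit.

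The sampling plan places the HPV sample elsewhere:

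- Protocol 9.1.1.2, on HPV antibody: "This assay will be performed on blood samples taken from V01, V02 and V05". The months given in Protocol 5.1.3 agree: "28 days after each vaccination with Cervarix (M1 and M7".
- Protocol Table 7.1 gives Group 2 a 2 mL draw at V05 (HPV only) and a 4 mL draw at V06 (dengue only).
- Protocol 5.1.4 gives Cervarix dose 2 at V04 in both groups, and CYD dose 2 at V04 in Group 1 and V05 in Group 2. A footnote to the Table of Study Procedures fixes the order within a visit: "Blood samples planned during vaccination visits will be taken before vaccination".

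SAP 5.2.5 runs the main Cervarix non-inferiority tests on PPX. Protocol 12.2.5 planned to confirm them on the full set of dengue-exposed subjects, but SAP 5.7 drops that set.

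**The concern.** The 28-day sample after Cervarix dose 2 is V05 in both arms, yet for Group 2 the rule inspects a visit that produces no HPV result. This has two consequences.

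First, read literally, a Group 2 girl with a valid V05 titre can be removed because her V06 draw was off-window, because she received a wrong product at V05 after the blood was taken, or because she took a prohibited medication after the draw. None of these can change the titre. Group 1 has no corresponding exposure, since its criteria end at the endpoint visit.

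Second, the timing of Group 2's actual HPV sample is not checked directly. It is reached only through the window for CYD dose 2, which the study tables anchor to V02 and not to Cervarix dose 2.

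At stake is the comparability of the arms in the population for the HPV co-primary GMT tests and the secondary seroconversion test. Each Group 2 subject lost this way also counts against the 163 and 168 evaluable per group that decide whether testing is done at all.

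**Working it through.** **1. The plan's own power figures** (SAP 5.5: one-sided alpha 2.5%, no true difference).

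GMT: power = Φ(0.301 / (SD·√(2/n)) − 1.96), multiplied over the six endpoints with SDs 0.4, 0.4, 0.9, 0.7, 0.7 and 0.5.

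- n = 204: 0.9219 × 0.9914² ≈ 90.6% (the other three terms round to 1); stated 90.2%.
- n = 163: 0.8553 × 0.9727² × 0.9997 ≈ 80.9%; stated 80.3%.

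Seroconversion: 99% in both groups, margin 5%, Farrington–Manning, power = Φ((0.05 − 1.96·s0)/s1). Here s0 is the standard error at the restricted maximum-likelihood null rates (0.9946 and 0.9446), and s1 = √(2 × 0.99 × 0.01/n).

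- n = 204: s0 = 0.01681, s1 = 0.00985; 95.8% per antigen, squared 91.8%; stated 91.8%.
- n = 168: s0 = 0.01852, s1 = 0.01086; 89.6% per antigen, squared 80.4%; stated 80.4%.

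The stated powers reproduce. The defect lies in who enters PPX.

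**2. Which visit carries the HPV endpoint**

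| | Group 1 | Group 2 |
|---|---|---|
| Cervarix dose 2 | V04 | V04 |
| HPV blood after dose 2 (Table 7.1) | V05 | V05 |
| V06 blood | none | dengue only |
| Visit named in PPX | V05 | V06 |

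Planned time from Cervarix dose 2 to V06 in Group 2 is 28 + 28 = 56 days. The endpoint is at 28 days.

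**3. Length of post-endpoint scrutiny**

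V06 is V05 + 28 days, window +14. Group 2 is therefore judged for a further 28 to 42 days after its HPV draw, and Group 1 for 0 days. The V05 injection in Group 2 also opens a new four-week prohibited-therapy period (Protocol 6.7) after the draw; Group 1 has no injection at V05.

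**4. The timing of V05**

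Three statements exist:

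- Study tables: "M7 (V04+28D) (Group 1) (V02+6M) (Group 2", window +14 days.
- Protocol 5.1.4: "Visit 5 (Month 7; 6 months /± 20 days/ after Visit 2", with no group split.
- Table 7.1: V04 + 28 days, window +14, with no group split.

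Under the study tables, V02 = V01 + 28 to 42 days and V04 = V01 + 6 months ± 20 days; in Group 2, V05 = V02 + 6 months + 0 to 14 days. Treating both six-month periods as equal, V05 − V04 is:

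- Group 1: 28 to 42 days.
- Group 2, maximum: 42 + 14 + 20 = 76 days.
- Group 2, arithmetic minimum: 28 + 0 − 20 = 8 days.

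The minimum conflicts with Protocol 5.1.2, which has the vaccines given "concomitantly or sequentially with Cervarix at least 28 days apart". The 5.1.4 text, with V04 at ± 20 days, gives 28 − 20 − 20 = −12 to 42 + 20 + 20 = 82 days. Table 7.1 gives 28 to 42 days in both groups. The statements cannot all hold and must be reconciled. The 76 days is an individual extreme, not a shift in the mean; planned sampling is about 28 days after dose 2 in both arms.

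**5. What losses would do**

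The documents give no rate of V06 deviations, so the losses below are assumed. Group 1 is held at 168, and power is exact for the planned Newcombe–Wilson interval, both antigens (per-antigen power squared).

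| Extra Group 2 loss | Group 2 n | Global power |
|---|---|---|
| 0% | 168 | 84.0% |
| 1% | 166 | 83.8% |
| 5% | 159 | 83.1% |
| 10% | 151 | 82.3% |

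HPV GMT power stays above 99.9% throughout. Any loss from exactly 168 puts Group 2 under the gate for the secondary test. From 240 per group, the gates leave room for 240 − 163 = 77 and 240 − 168 = 72 losses from all causes, including baseline dengue-seronegative subjects.

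**The case against.** The strongest reply is that the effect is small. No V06 HPV titre exists that could be analysed by mistake, and a wholly missing V05 result should still be caught by the last PPX bullet, which is tied to no visit. A missed V06 is unlikely: the protocol synopsis reports that "all subjects have completed V05 (Group 1) or V06 (Group 2". The remaining routes to a wrongful exclusion are narrow, and the power loss is slight even at an assumed 10%. All of this stands, and it limits the weight of the point.

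A second reply is that V05/V06 follows each arm to the visit 28 days after its second CYD dose, so the later horizon may be deliberate and fits the prohibited-therapy windows. That could explain the vaccination and medication bullets. It cannot explain a bullet about a sample after Cervarix, and what happens after a blood draw does not bear on the titre in that blood. The SAP also narrows the schedule bullet to the Cervarix schedule, where the protocol does not.

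Third, full-analysis-set HPV results by dengue serostatus will still be reported with confidence intervals (SAP 5.1.2.2 and 5.2.5), so a difference from PPX could be seen. This is true, but they are descriptive; no second non-inferiority test remains.

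Finally, the 76-day figure comes from the visit schedule and arises under one of the three V05 definitions. The 77 and 72 cover all losses and do not measure this defect. Both points are accepted.

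**Conclusion.** The concern holds and should be fixed. The PPX rule as written names the wrong visit for one arm and exposes only that arm to exclusion for 28 to 42 days of events after its endpoint. This is a contradiction within the documents; it does not depend on an assumed rate. The number of subjects affected and the direction of any bias cannot be obtained from the documents, and neither is claimed. The power effect is small under the assumed losses (84.0% to 82.3% at 10%). The practical risks are an avoidable challenge to the main Cervarix population and, if numbers are close to 163 or 168, a decision on testing that turns on subjects removed without good reason.

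**What to change.** - In PPX, name V05 for both groups, and apply the product, timing, site/route, sample and medication criteria only up to the V05 HPV draw.
- Reconcile the three V05 timing statements. Then judge the HPV sample by one rule, identical in both arms and counted from the actual date of Cervarix dose 2. Settle that rule before HPV titres are looked at by group, since the trial is open-label.
- Tabulate the actual interval from dose 2 to sample by group, and add a sensitivity analysis limited to samples at 28 to 42 days. Keep that limit out of the PPX definition: as a hard exclusion it would remove Group 2 subjects who followed the study table.
- Record all of this in SAP 5.7 as a change from Protocol 12.2.2.

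The cost is a small SAP revision and some programming on data already collected. The PPX count may move slightly against the 163 and 168 thresholds.
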